Timepoint	Dose (Group A)	Dose (Group B)
Starting dose	20 mg QD for 8 weeks (Day 1 through Day 56)	20 mg QD for 8 weeks (Day 1 through Day 56)
First dose reduction	10 mg QD	10 mg QD
Second dose reduction	5 mg QD	5 mg QD
Week 9 (Day 57) onward	20 mg once weekly ^a	2.5 mg QD ^b
First dose reduction	10 mg once weekly	1 mg QD ^c
Second dose reduction	5 mg once weekly	NA

^a All subjects will receive 20 mg once weekly at Week 9 (Day 57) regardless of prior dose level, unless a dose modification of a switch to a QW schedule before Week 9 is required for diarrhea/colitis management (see [Table 5](#)).

^b All subjects will receive 2.5 mg QD at Week 9 (Day 57) regardless of prior dose level, unless a dose modification of a switch to a QW schedule is required for diarrhea/colitis management (see [Table 5](#)).

^c Further dose modification due to diarrhea or colitis for subjects on 1 mg QD is permitted (see [Table 5](#)).

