
 Diarrhea (≥ Grade 3). Noninfectious colitis (any grade; confirmed or suspected). 	
Step 1: Interrupt INCB050465. Perform work-up for infection (including CMV, C. difficile, etc) immediately. Initiate or continue supportive care (see Section 5.4.1.2). Consider colonoscopy with biopsy for diarrhea ≥ Grade 3 and/or if symptoms^a suggestive of colitis. Monitor every 48 hours until resolution.
 
Step 2: If infection* is ruled out, start oral steroids, or consider IV steroids if participant is being given IV fluids. If no improvement with oral steroids within 48 hours, switch to IV steroids.
 
*For infectious diarrhea/colitis, follow institutional standard of care guidelines and restart pascalisib according to clinical judgement after resolved to ≤ Grade 1. Consult with medical monitor if needed.
 
Step 3: When diarrhea/colitis resolves to ≤ Grade 1, continue supportive care and taper steroids according to institutional standard of care. When taper is complete (eg, no steroid or ≤ 10 mg/day prednisone or equivalent) and diarrhea/colitis is ≤ Grade 1, restart INCB050465 as described herein and with approval of the medical monitor. Continue to monitor.
 
  
 INCB050465 Current Dose	Dose Modification	
   
 Any dose with QD dosing	20 mg QW regardless of Treatment A or B assignment	
 
 20 or 10 mg QW	Restart next lower dose	
 
 5 mg QW	Permanently discontinue	
  
 
Step 4: If ≥ Grade 3 diarrhea/colitis (any grade) reoccurs, permanently discontinue INCB050465.
	INCB050465 Current Dose	Dose Modification	Any dose with QD dosing	20 mg QW regardless of Treatment A or B assignment	20 or 10 mg QW	Restart next lower dose	5 mg QW	Permanently discontinue
INCB050465 Current Dose	Dose Modification								
Any dose with QD dosing	20 mg QW regardless of Treatment A or B assignment								
20 or 10 mg QW	Restart next lower dose								
5 mg QW	Permanently discontinue								

^a Diarrhea accompanied by abdominal pain and/or mucus or blood in stool.

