## 6.4. Exposure

For participants in the safety population, exposure to INCB050465 will be summarized descriptively as the following:

• **Duration of treatment (days)**: Date of last dose – date of first dose + 1.

- **Duration of treatment during the initial QD dosing period (days)**: Date of last dose during initial QD dosing period date of first dose + 1.
- Duration of treatment during the maintenance dosing period (days): Date of last dose date of first dose during the maintenance dosing period + 1. Crossover participants who switched to the selected treatment regimen after the start of the maintenance dosing period will be summarized in a separate group (ie, Crossover).
- Average reported daily dose during the initial QD dosing period (mg/day): Total reported dose taken during initial QD dosing period (mg) / duration of treatment during the initial QD dosing period (days).
- Average reported daily dose during the maintenance dosing period (mg/day): Total reported dose taken during the maintenance dosing period (mg) / duration of treatment during the maintenance dosing period (days). Crossover participants who switched to the selected treatment regimen after the start of the maintenance dosing period will be summarized in a separate group (ie, Crossover).
- **Dose modifications:** Number of participants who had dose reduction and interruption will be summarized. The number of dose reductions and the number of interruptions for each participant will be summarized.

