#### 9.2.3. Adverse Event Summaries

Overall summaries of TEAEs by treatment regimen will be provided during the INCB050465 initial QD dosing period, maintenance dosing period, and overall period (ie. all TEAEs regardless of the timing of occurrence). These summaries will include the following:

- Number (%) of participants reporting any TEAEs
- Number (%) of participants reporting any Grade 3 or higher TEAEs
- Number (%) of participants reporting any serious TEAEs
- Number (%) of participants reporting any TEAEs related to INCB050465
- Number (%) of participants reporting any Grade 3 or higher TEAEs related to INCB050465
- Number (%) of participants reporting any serious TEAEs related to INCB050465

- Number (%) of participants who had TEAE with fatal outcome
- Number (%) of participants with INCB050465 dose reductions because of TEAEs
- Number (%) of participants who temporarily interrupted INCB050465 because of TEAEs
- Number (%) of participants who permanently discontinued INCB050465 because of TEAEs

The following summaries will be produced for TEAEs during the overall period by MedDRA term (if 10 or fewer participants appear in a table, a listing may be appropriate):

- Summary of TEAEs by SOC and PT
- Summary of TEAEs by PT in decreasing order of frequency
- Summary of TEAEs by SOC, PT, and maximum severity
- Summary of TEAEs by PT and maximum severity in decreasing order of frequency
- Summary of Grade 3 or higher TEAEs by SOC and PT
- Summary of Grade 3 or higher TEAEs by PT in decreasing order of frequency
- Summary of serious TEAEs by SOC and PT
- Summary of serious TEAEs by PT in decreasing order of frequency
- Summary of INCB050465 treatment-related TEAEs by SOC and PT
- Summary of INCB050465 treatment-related TEAEs by PT in decreasing order of frequency
- Summary of INCB050465 treatment-related TEAEs by SOC, PT, and maximum severity
- Summary of Grade 3 or higher INCB050465 treatment-related TEAEs by SOC and PT
- Summary of INCB050465 treatment-related serious TEAEs by SOC and PT
- Summary of TEAEs with a fatal outcome by SOC and PT
- Summary of TEAEs leading to INCB050465 dose reduction by SOC and PT
- Summary of TEAEs leading to INCB050465 dose interruption by SOC and PT
- Summary of TEAEs leading to discontinuation of INCB050465 by SOC and PT
- Summary of selected TEAEs of special interest by maximum severity
- Summary of time to onset of selected TEAEs of special interest

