2.4.7	Summary of Progression-Free Survival as Determined by Independent Review Committee – Censoring Crossover Participants	FAS	
2.4.8	Summary of Progression-Free Survival as Reported by Investigator – Censoring Crossover Participants	FAS	
Safety			
3.1.1	Summary of Exposure and Compliance	Safety	
3.1.2	Summary of Exposure and Average Daily Dose During Initial QD Dosing Period	Safety	
3.1.3	Summary of Exposure and Average Daily Dose During Maintenance Dosing Period	Safety	
3.2.1	Overall Summary of Treatment-Emergent Adverse Events	Safety	X
3.2.2	Summary of Treatment-Emergent Adverse Events by MedDRA System Organ Class and Preferred Term	Safety	X
3.2.3	Summary of Treatment-Emergent Adverse Events by MedDRA Preferred Term in Decreasing Order of Frequency	Safety	X
3.2.4	Summary of Treatment-Emergent Adverse Events by MedDRA System Organ Class, Preferred Term, and Maximum Severity	Safety	X
3.2.6	Summary of Grade 3 or Higher Treatment-Emergent Adverse Events by MedDRA System Organ Class and Preferred Term	Safety	X
3.2.7	Summary of Grade 3 or Higher Treatment-Emergent Adverse Events by Preferred Term in Decreasing Order of Frequency	Safety	X
3.2.8	Summary of Serious Treatment-Emergent Adverse Events by MedDRA System Organ Class and Preferred Term	Safety	X
3.2.9	Summary of Serious Treatment-Emergent Adverse Events by Preferred Term in Decreasing Order of Frequency	Safety	X
3.2.10	Summary of INCB050465 Treatment-Related Treatment-Emergent Adverse Events by MedDRA System Organ Class and Preferred Term	Safety	X
3.2.11	Summary of INCB050465 Treatment-Related Treatment-Emergent Adverse Events by MedDRA Preferred Term in Decreasing Order of Frequency	Safety	X

Table No.	Title	Population	Standard
3.2.12	Summary of INCB050465 Treatment-Related Treatment-Emergent Adverse Events by MedDRA System Organ Class, Preferred Term, and Maximum Severity	Safety	X
3.2.14	Summary of Grade 3 or Higher INCB050465 Treatment-Related Treatment-Emergent Adverse Events by MedDRA System Organ Class and Preferred Term	Safety	X
3.2.15	Summary of INCB050465 Treatment-Related Serious Treatment- Emergent Adverse Events by MedDRA System Organ Class and Preferred Term	Safety	X
3.2.16	Summary of Treatment-Emergent Adverse Events With a Fatal Outcome by MedDRA System Organ Class and Preferred Term	Safety	X
3.2.18	Summary of Treatment-Emergent Adverse Events Leading to INCB050465 Dose Reduction by MedDRA System Organ Class and Preferred Term	Safety	X

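### Do the dose-reduction counts go wrong because the SAP has no category for the Protocol Table 5 switch from daily to weekly dosing?

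*SAP*

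**What the plan says.** SAP 6.4 plans two dose-modification summaries. The first is at participant level: "Number of participants who had dose reduction and interruption will be summarized". The second was added by SAP Amendment 2: "The number of dose reductions and the number of interruptions for each participant will be summarized". SAP 9.2.3 carries the same scheme into the adverse-event overview, with a row for "Number (%) of participants with INCB050465 dose reductions because of TEAEs" and further rows for interruption and permanent discontinuation. Appendix A has matching tables by system organ class and preferred term; Table 3.2.18 is "Summary of Treatment-Emergent Adverse Events Leading to INCB050465 Dose Reduction by MedDRA System Organ Class and Preferred Term". The SAP neither defines a dose reduction nor mentions a change from daily to weekly dosing.

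Protocol Table 5 contains such a change. After Grade 3 or higher diarrhea or noninfectious colitis, a participant on any daily dose restarts at "20 mg QW regardless of Treatment A or B assignment". A participant already on 20 or 10 mg weekly follows a different rule: "Restart next lower dose". Recurrent Grade 2 diarrhea is managed under the same rules.

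Protocol Table 4 lists 10 and 5 mg once weekly as the Group A maintenance reductions, and 1 mg daily as the only Group B one. Its footnotes set the switch apart from those levels. Group B receives 2.5 mg daily from Week 9 "unless a dose modification of a switch to a QW schedule is required for diarrhea/colitis management", and for the lowest Group B level, "Further dose modification due to diarrhea or colitis for subjects on 1 mg QD is permitted".

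**The concern.** The SAP counts three consequences of an adverse event: reduction, interruption and discontinuation. The protocol has a fourth for the toxicity it manages in most detail. In maintenance, one event gives a listed reduction in Group A and a change of schedule in Group B.

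If the switch is not counted, a Group B participant taken off daily dosing for colitis can show no dose reductions and an average daily dose close to nominal, and the combined reduction row adds two groups whose events led to different kinds of step. Group B is the selected regimen (SAP 11.2, Amendment 1), and the per-participant counts came in with an amendment written to answer FDA comments. A reader comparing reduction rows might take Group B to be better tolerated than it is.

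**Working it through.** The plan states no figure on this point, so there is none to reproduce. The check asks whether the Group B step is a reduction on any reasonable basis, and then where the event appears in the planned output.

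**Inputs.** Maintenance doses, 20 mg weekly (A) and 2.5 mg daily (B): Protocol Table 2 and SAP 5.2. Reduction levels: Protocol Table 4. Steps after each event: Protocol Table 5.

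**Formula.** Weekly dose = daily dose × 7, or the dose itself if weekly. Change = after / before − 1.

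| Step | Weekly mg | Change | Dose per intake | Table 4 reduction level? |
|---|---|---|---|---|
| A maintenance, 20 to 10 mg weekly | 20 to 10 | 10/20 − 1 = −50% | 20 to 10 | Yes |
| B maintenance, 2.5 mg daily to 20 mg weekly | 17.5 to 20 | 20/17.5 − 1 = +14.3% | 2.5 to 20 | No |
| B maintenance, 1 mg daily to 20 mg weekly | 7 to 20 | 20/7 − 1 = +185.7% | 1 to 20 | No |
| First 8 weeks, both groups, 20 mg daily to 20 mg weekly | 140 to 20 | 20/140 − 1 = −85.7% | 20 to 20 | No |
| B, first unresolved noninfectious Grade 2 diarrhea, 2.5 to 1 mg daily | 17.5 to 7 | 7/17.5 − 1 = −60% | 2.5 to 1 | Yes |

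Three results follow.

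1. The Group B maintenance switch is not a reduction by weekly dose, by dose per intake or by Table 4 level. A count of zero misstates nothing.
2. The difference between groups is confined to Grade 3 or higher diarrhea, noninfectious colitis and recurrent Grade 2 diarrhea. A first unresolved noninfectious Grade 2 diarrhea leads to a listed reduction in both groups (10 mg weekly in A, 1 mg daily in B).
3. The basis of counting matters only in the first 8 weeks, where the weekly dose falls 86% and the dose per intake is unchanged. Both groups then have the same dose and the same rule, so the ambiguity does not favor either.

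**What the exposure table would show (timing assumed).** Event at the end of Week 16, 28-day interruption, dosing to Week 52. Maintenance starts on Day 57 and dosing restarts on Day 141. The last of 32 weekly doses falls on Day 358, so duration is 358 − 57 + 1 = 302 days.

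- Group A: (8 × 20 + 32 × 10) / 302 = 480/302 = 1.59 mg/day, 44% below the nominal 20/7 = 2.86.
- Group B: (56 × 2.5 + 32 × 20) / 302 = 780/302 = 2.58 mg/day, 3% above the nominal 2.5.

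With interruptions of 14 to 56 days, Group A is 42% to 49% below nominal, and Group B runs from 9% above to 7% below. These averages correctly describe the drug received.

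**Where the event still appears.** Table 5 begins with an interruption for all three triggers, so each enters the SAP 6.4 interruption counts, the SAP 9.2.3 interruption row and Table 3.2.19. Diarrhea and colitis enter the special-interest summaries of severity, time to onset and longest duration (Tables 3.2.26 to 3.2.29). Listings 2.5.2 (drug administration) and 2.7.6 (events leading to interruption, reduction or discontinuation) can show individual cases.

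**Size.** Planned Group B = 25 + 70 = 95. One switch counted or not moves its reduction row by 1/95 = 1.05 points.

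**The case for a change.** The strongest case for a change is that the SAP is based on Protocol Amendment 9, which revised the diarrhea and colitis rules, yet neither later SAP amendment took up the switch. No planned summary table isolates it. Sites could code it differently, some as a reduction and some not. SAP 5.2 also groups by regimen actually received, and its special rules cover only a move to the selected regimen. A Group B participant switched before Week 9 has in effect followed Group A's schedule, and the SAP does not say where that person is tabulated. The remedy would be cheap.

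Part of this stands. The term is undefined, and a separate row for the switch would be informative. But it is not established that the switch goes uncounted in Group B. The SAP is silent, and neither the CRF nor the table shells are in the documents. The CRF approval date, 405 days before Amendment 9, proves nothing: SAP 2.1 extends to later CRF versions, and Group A's planned move to weekly dosing made frequency relevant throughout.

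On grouping, Table 4 treats the switch as a dose modification, and Table 5 applies it whatever the assignment. The sensible reading, though an inference, is that the participant stays in the assigned group. The combined ORR does not depend on it.

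Nor do the documents present the reduction count as the key tolerability measure. Protocol 1.4 justifies both maintenance regimens by fewer adverse events leading to treatment withdrawal, and discontinuations are counted in full.

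**Conclusion.** No change to the plan is needed. The gap is one of detail, and a competent analyst fills it when specifying the tables: count reductions by the Table 4 levels, and show the switch separately if any occur. Appendix A allows its lists and shells to be modified without a SAP amendment when the nature of the analysis is unaffected.

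Followed as written, the plan produces no false result. The unequal reduction counts in maintenance reflect the protocol's different steps for the two groups, and the planned interruption and adverse-event output covers the underlying event. No between-group comparison is planned (SAP 3.2), so no inference rests on the difference between the two reduction rows. The effect is limited to descriptive exposure and dose-modification rows, at about 1.1 points per Group B switch.

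This rests on three assumptions: the dosing record captures frequency, a switched participant stays in the assigned group, and switches are not so numerous that the reduction row would mislead without a note. The documents do not give their number. Nothing here bears on the dosing rules themselves.

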# 6.5. Study Drug Compliance

For participants in the safety population, overall compliance (%) for INCB050465 will be calculated for all participants as

compliance (%) =  $100 \times [\text{total dose actually taken}] / [\text{total prescribed dose}].$ 

The total prescribed dose is defined as the sum of the doses prescribed by the investigator accounting for dose modifications.

The total actual dose taken will be calculated based on information entered on the Drug Accountability CRF. If there are dispensed drugs that have not been returned yet, the actual dose taken starting from the dispense date of the unreturned drugs will be imputed by the dose taken as reported on the dosing CRF.

#### 6.6. Prior and Concomitant Medication

Prior medications and concomitant medications will be coded using the WHO Drug Dictionary. Number and percentage of participants in the FAS for each prior and concomitant medication will be summarized by WHO drug class and WHO drug PT.

#### 7. EFFICACY

Appendix A provides a list of planned tables, figures, and listings. Sample data displays are included in a separate document.

# 7.1. Efficacy Hypotheses

Not applicable.

# 7.2. Response Assessment

An objective assessment of disease status is required at baseline (screening) using the CT-based response criteria of the Lugano Classification (Cheson et al 2014). Disease status will be subsequently assessed by CT/MRI every 8 weeks through Week 24, then every 12 weeks through Week 96, and then every 24 weeks thereafter until disease progression.

Bone marrow examination is required as a baseline assessment at screening except for reasons provided in Section 7.6.2 of the Protocol. If disease is present in bone marrow at baseline, a bone marrow examination will be required to confirm CR or may be performed as clinically indicated. If the bone marrow does not have lymphoma involvement at baseline, a repeat marrow examination is not required to confirm indication of CR on imaging.

Sites will use the CT-based response criteria of the Lugano Classification (Cheson et al 2014) to assess response to treatment locally. At each postbaseline disease assessment, response will be collected in the eCRF as CR, PR, SD, PD, or NE.

All imaging will be submitted to the IRC. Imaging data and applicable clinical data will be reviewed and response will be assessed using the CT-based response criteria of the Lugano Classification (Cheson et al 2014) by independent reviewers as described in the Independent Review Charter. An overall timepoint response at each postbaseline disease assessment, the best overall response, the date of initial response (if applicable), and the date of progression along with the reason(s) of disease progression (if applicable) for each participant, considering radiographic data and clinical data, will be provided by Clinical Reviewer. These data will be used in the analyses of related efficacy endpoints.

# 7.3. Analysis of the Primary Efficacy Parameter

The primary efficacy analyses will be conducted when all participants in the FAS who have achieved a response (ie, PR or CR) according to the IRC have had approximately 12 months of follow-up from the onset of response.

#### 7.3.1. Best Overall Response and Overall Response Rate

For responses determined by the IRC, the best overall response for each participant will be provided by the Clinical Reviewer. A participant is considered an objective responder if they have a best overall response of CR or PR.

The ORR is the proportion of objective responders. Participants who do not have sufficient baseline or on-study response assessment information to be adequately assessed for response status will be included in the denominators in the calculation of ORR.

Best overall response as determined by the IRC will be descriptively summarized by treatment groups and combined. The ORR as determined by the IRC will be estimated with 95% CIs. Confidence intervals will be calculated based on the exact method for binomial distributions.

Because participants who switched to the selected treatment regimen after starting the maintenance dose received a mixture of the non-selected and selected maintenance regimens and could confound the efficacy evaluation of the non-selected treatment regimen, a sensitivity analysis of ORR as determined by IRC will be provided to summarize these crossover participants as a separate treatment regimen. In addition, the number of participants who achieved best overall response as determined by IRC after the time of crossover along with the best overall response data will be presented under this separate treatment regimen.

When applicable, sensitivity analysis of ORR as determined by the IRC may be provided excluding participants that do not have evaluable radiological images at baseline per the IRC.

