4. INVESTIGATIONAL PLAN

4.1. Overall Study Design

This is a Phase 2, multicenter, open-label study evaluating 2 INCB050465 treatment regimens based on the primary endpoint of ORR. Subjects with relapsed or refractory FL (Grades 1, 2, or 3a) who have received at least 2 prior systemic therapies and who are ineligible for HSCT will be screened for eligibility. A total of approximately 120 subjects will be enrolled. The first 50 subjects enrolled will be assigned at a 1:1 ratio to treatment Group A (INCB050465 20 mg QD for 8 weeks followed by 20 mg once weekly) and treatment Group B (INCB050465 20 mg QD for 8 weeks followed by INCB050465 2.5 mg QD; see [Figure 2](#)). The remaining 70 subjects will be allocated to one of the 2 treatment groups to better understand the safety and efficacy of that treatment regimen. The treatment group will be selected after evaluation of emerging safety and efficacy data from this and other monotherapy studies of INCB050465 in NHL that are evaluating the same or similar dosing regimens and will be implemented after the first 50 subjects are enrolled. Subjects allocated to the non-selected treatment regimen may switch to the selected treatment regimen or remain on their current treatment regimen, provided they have not met study-treatment withdrawal criteria, and there are no safety concerns for their current treatment regimen. There will be no re-baselining for subjects who switch treatment regimens, and all subjects will continue to follow the same assessment schedule. Furthermore, no changes will be made to the primary analysis. The study treatments will be administered orally.

[figure not shown]
Subjects will be evaluated for ORR by an IRC and followed for CRR, DOR, PFS, OS, and safety. Subjects may receive treatment until disease progression, death, unacceptable toxicity, or consent withdrawal.

An interim futility analysis is planned when the first 50 subjects have been evaluated for response or have permanently discontinued study treatment because of disease progression, withdrawal of consent, or death. The study will be terminated for futility if ≤ 18 of the 50 subjects have responded (ie, CR or PR) based on assessments provided by the IRC; otherwise the study will continue. A timely assessment of response will be performed to avoid the risk of overenrollment.

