#### 3. STUDY DESIGN

This is a Phase 2, multicenter, open-label study evaluating 2 INCB050465 treatment regimens based on the primary endpoint of ORR. Participants with relapsed or refractory FL (Grades 1, 2, or 3a) who have received at least 2 prior systemic therapies and who are ineligible for hematopoietic stem cell transplant will be screened for eligibility. A total of approximately 120 participants will be enrolled. The first 50 participants enrolled will be assigned at a 1:1 ratio to 2 study treatment regimens as follows (see Figure 1):

- Group A: INCB050465 20 mg QD for 8 weeks followed by 20 mg once weekly
- Group B: INCB050465 20 mg QD for 8 weeks followed by 2.5 mg QD

[figure not shown]
The remaining 70 participants will be allocated to 1 of the 2 treatment groups to better understand the safety and efficacy of that treatment regimen. The treatment group will be selected after evaluation of emerging safety and efficacy data from this and other monotherapy studies of INCB050465 in NHL, which are evaluating the same or similar dosing regimens, and will be implemented after the first 50 participants are enrolled. Participants allocated to the nonselected treatment regimen may switch to the selected treatment regimen or remain on their current treatment regimen, provided they have not met study-treatment withdrawal criteria, and there are no safety concerns for their current treatment regimen. There will be no rebaselining for participants who switch treatment regimens, and all participants will continue to follow the same assessment schedule.

Participants may receive treatment until disease progression, death, unacceptable toxicity, or consent withdrawal, whichever occurs first. Participants will be evaluated for ORR by an IRC and followed for CRR, DOR, PFS, OS, and safety.

An interim futility analysis is planned when the first 50 participants (Group A and Group B combined) have been evaluated for response or have permanently discontinued study treatment because of disease progression, withdrawal of consent, or death. The study will be terminated

for futility if  $\leq$  18 of the 50 participants have responded (ie, CR or PR) based on assessments provided by the IRC.

Figure 1: Study Design

<sup>a The first 50 subjects will be assigned at a 1:1 ratio to treatment Group A and treatment Group B. The remaining 70 subjects will be enrolled to the selected treatment Group (ie, either Group A or Group B).

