# **3.3.** Sample Size Considerations

Approximately 120 participants will be enrolled and assigned to either treatment Group A or Group B. The first 50 participants will be assigned at a 1:1 ratio to 2 treatment groups, and the remaining 70 participants will be allocated to the selected treatment group based on the emerging safety and efficacy data from this and other monotherapy studies of INCB050465 in NHL that are evaluating the same or similar dosing regimens. If the true ORR is 51% for participants in Group A and Group B, then with 120 total participants, there is approximately 93% probability of observing the lower bound of the 95% CI of ORR  $\geq$  35%.

bA futility analysis will be performed when the first 50 subjects have been evaluated for response.

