# **5.2.** Treatment Groups

This is a Phase 2, multicenter, open-label study. For the purpose of analysis, the 20 mg once weekly dosing period in Group A and the 2.5 mg QD dosing period in Group B are considered maintenance dosing periods. Data will be presented in summary tables by actual received treatment regimen and combined, with an exception for participants who cross over to the selected treatment regimen after the start of the maintenance dosing period. There will not be any statistical comparison between the treatment groups.

For participants who cross over from the initially assigned treatment regimen to the selected treatment regimen, if the crossover happens on/before the start of the maintenance period, then the participant will be summarized, according to the actual received treatment, in the selected treatment regimen; otherwise, the participant will be summarized in:

- A separate treatment regimen (ie, Crossover) for the safety summaries during the maintenance dosing period (eg. summaries of TEAEs and exposure).
- The initially assigned treatment regimen for all other summaries.

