# 11.1. Changes to Protocol-Defined Analyses

The PP population was removed from the planned analysis. For a single-arm, open-label study, the determination of participants to be excluded from the PP population is post hoc and may not be done objectively; thus, analysis based on this population may not be meaningful.

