#### **Amendment 1 (26 AUG 2020)**

- Section 3 was modified to increase the target enrollment from approximately 100 to approximately 120 participants. This change is to align with recommendations from FDA.
- Section 4.1.4 was updated to include details of rules for handling partial/missing onset or end date of TEAEs in the calculation of time to onset or duration of a TEAE. Rules for partial/missing date of last dose were updated to include details for when both month and day are missing.
- Section 5.2 was modified to provide details regarding how crossover participants will be summarized.
- Section 5.3 was updated to add the all-screened population for the summary of analysis populations.
- Section 6.1.2 was updated to add relapsed/refractory status to the most recent prior therapy to the summary table of disease history because the response to last regimen before entering the study may be a prognostic factor for clinical outcomes.
- Section 6.2 was modified to add summaries of participants who are ongoing with treatment or still in the study.
- Section 6.4 was modified to change the calculations of duration of treatment and average dose during the maintenance dosing period because Group B with 2.5 mg QD was selected as the maintenance dose.
- Section 7.3 was updated to change the timing of the primary analysis to align with recommendations from FDA.
- Section 7.3.2 was modified to add "unknown" as a category for bone marrow involvement at baseline. Relapsed/refractory status to the most recent prior therapy was added to the subgroup analysis because the response to last regimen before entering the study may be a prognostic factor for clinical outcomes.
- Section 7.4.3 was modified to update references of censoring for PFS.

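### Does the SAP need to say which ORR interval (Group A, Group B or combined) is the primary one?

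*SAP*

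**What the plan says.** SAP 7.3.1 summarises IRC best overall response by treatment group and combined. It then states, without naming a group: "The ORR as determined by the IRC will be estimated with 95% CIs". SAP 5.2 sets the general display rule: "Data will be presented in summary tables by actual received treatment regimen and combined". Protocol 9.4.1.1 also speaks of the ORR and its exact interval without naming a group, and SAP 7.1 (efficacy hypotheses) is marked not applicable.

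Several places bear on which group is meant:

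- SAP 2.2, Table 1 states the primary objective for INCB050465, not for a regimen.
- SAP 5.3.2 and Protocol 9.1 assign all efficacy analyses to the full analysis set, which is every treated participant.
- SAP 3.3 gives the sample-size basis: "If the true ORR is 51% for participants in Group A and Group B, then with 120 total participants, there is approximately 93% probability" of a lower limit of at least 35%.
- SAP 10 and Protocol 9.6 apply the futility rule to Groups A and B combined.
- SAP 11.1 explains the loss of the per-protocol population with the words "For a single-arm, open-label study".
- Protocol 4.1, after describing the regimen selection and crossover, says: "Furthermore, no changes will be made to the primary analysis".

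Other text has a by-regimen flavour. SAP 3 describes a study "evaluating 2 INCB050465 treatment regimens based on the primary endpoint of ORR". The last 70 participants go to one regimen so that it is better understood. SAP 7.3.1 adds a crossover sensitivity analysis because switching "could confound the efficacy evaluation of the non-selected treatment regimen".

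**The concern.** A primary endpoint should have one designated estimate. Here the same endpoint is displayed three ways, no hypothesis fixes the choice, and Protocol 4.1's sentence keeping the primary analysis unchanged is not repeated in the matching paragraph of SAP 3. The SAP can be explicit when it wishes: in 7.4.5 it says that the waterfall plot combines the two groups.

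Timing sharpens the worry. The study is open-label, the regimen was to be chosen partly on emerging efficacy data from this trial, and SAP 11.2 (Amendment 1) already records that "Group B with 2.5 mg QD was selected as the maintenance dose". If the primary interval were truly open, the headline could be the combined result on about 120 or the selected-regimen result on about 25 + 70 = 95, whichever read better against 35%, the only benchmark in the plan.

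**Working it through.** **Inputs.** N = 120 in total, true ORR 51%, benchmark 35% (SAP 3.3). Two-sided 95% intervals (SAP 3.2) by the exact binomial method (SAP 7.3.1). First 50 split 1:1, taken as 25 and 25; the next 70 all go to the selected regimen, giving n = 95 (SAP 3.3). Stop if 18 or fewer of the first 50 respond (SAP 10). Non-evaluable participants stay in the denominator (SAP 7.3.1). A true ORR of 45% is an assumption for illustration and is not in the documents.

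**Step 1: cut-offs.** The exact lower limit is L(x, n) = the 2.5% quantile of Beta(x, n − x + 1).

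- Combined: L(53, 120) = 0.3511 and L(52, 120) = 0.3432, so 53 responders are needed.
- Selected: L(43, 95) = 0.3502 and L(42, 95) = 0.3402, so 43 responders are needed.

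**Step 2: the plan's own figures.**

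- P(X ≥ 53 | n = 120, p = 0.51) = 94.4%. Requiring also at least 19 responders in the first 50 gives 93.1%, which matches the stated 93%.
- P(X ≤ 18 | n = 50) = 62.16% at p = 0.35 and 2.34% at p = 0.51, as SAP 10 states.

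The sample-size statement is therefore correct, and it is a statement about the combined 120.

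**Step 3: how often the two intervals disagree.** Let A ~ Bin(25, p) be responders on the non-selected regimen, B1 ~ Bin(25, p) first-stage responders on the selected regimen, and B2 ~ Bin(70, p) second-stage responders. Sum the joint probabilities over A + B1 ≥ 19. Combined clears 35% if A + B1 + B2 ≥ 53; selected clears it if B1 + B2 ≥ 43. With the regimen choice independent of responses, as a share of all trials:

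| True ORR | Combined clears | Selected clears | Combined only | Selected only | Opposite sides |
|---|---|---|---|---|---|
| 45% (assumed) | 58.6% | 48.3% | 12.4% | 2.2% | 14.6% |
| 51% (planned) | 93.1% | 87.4% | 6.3% | 0.5% | 6.8% |

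At 59% the intervals disagree in 0.2% of trials.

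**Step 4: which disagreement would matter.** If combined is the planned reading, moving to the selected regimen gains something only in the selected-only column: 0.5% at 51% and 2.2% at 45%. The combined-only column is largely the precision difference between 120 and 95.

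**Step 5: sensitivity to the conditions.**

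- Without the futility stop, opposite sides: 7.1% at 51% and 16.3% at 45%.
- If the regimen with the higher ORR in the 25 v 25 comparison were chosen, with the stop: 2.7% at 51% (combined only 1.65%, selected only 1.0%) and 8.5% at 45% (4.1% and 4.3%).
- If five early crossovers are counted in the selected group under SAP 5.2 (an assumed number, n = 100), ignoring the stop: 5.7% at 51% and 14.1% at 45%.
- With unequal true ORRs, ignoring the stop: 7.7% if A is 40% and B is 51%; 21.5% if A is 51% and B is 45%. In the second case it is almost all combined-only (20.2%, against 1.3% selected-only).

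**Step 6: the by-regimen wording.** Describing a study of two regimens states the design. Learning more about one regimen from 70 further participants is a supportive aim. The crossover analysis is labelled a sensitivity analysis, and reclassifying crossovers moves people between regimen columns while leaving the combined ORR as it was. None of this makes a regimen-specific ORR primary.

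**The case for a change.** The strongest case for a change is that inference from several sections is weaker than a plain designation, that the regimen was picked with efficacy data in view, and that one sentence would cost almost nothing. It is true that neither document contains that sentence; even Protocol 4.1's statement that the primary analysis is unchanged does not name the group. It is also true that the plan gives no probability for the selected regimen alone (87.4% with the stop, 88.9% without, if the choice is independent of responses), and that the two intervals can disagree.

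That supports an optional wording note but does not show a defect. The omission from SAP 3 carries little weight: SAP 1 and 2.1 tie the SAP to Protocol Amendment 9, and SAP 11.1 lists departures from Protocol-defined analyses and names only the per-protocol population. The Protocol statement therefore still governs. Nor could a less favourable result be set aside unseen, because SAP 5.2 requires the regimen and combined results in the same summaries. Adding an operating characteristic for the selected regimen, or a separate row for the 70 enrolled after selection, would be a matter of preference; neither corrects an error.

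**Conclusion.** This is missing detail that an analyst would fill correctly: the primary result is the IRC ORR with its exact 95% interval in the full analysis set, Groups A and B combined, with the regimen-specific results supportive. Naming it would record the evident intent and alter no calculation, stated figure or result.

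The stakes are also small. At the planned ORR of 51% the selected regimen alone would clear 35% when combined did not in about 0.5% of trials (1.0% if the higher ORR decided the choice); at an assumed 45% the figures are 2.2% and 4.3%. These rest on a 25/25 split, exactly 120 treated, equal true ORR in both groups, no early crossovers counted in the selected group, and the futility stop applied. Moreover, 35% appears only in the sample-size statement and the futility operating characteristics. SAP 7.1 sets no hypothesis and Protocol 4.2 rules out comparison with historical controls, so crossing it affects interpretation and not a formal decision.
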